2. STUDY SUMMARY

PROTOCOL NO.: GS-LHON-CLIN-06
TITLE OF STUDY: Long-term Follow-up of ND4 LHON Subjects Treated With GS010 Ocular Gene Therapy in the RESCUE or REVERSE Phase III Clinical Trials
INVESTIGATIONAL CENTERS: The 7 investigational centers are located in the European Union (United Kingdom [1], France [1], Germany [1], and Italy [1]) and the United States (3) and will be the same centers as those used in the RESCUE and REVERSE studies.
STUDY PERIOD: The total study period for an individual subject will be 3 years. The study will be stopped when the last subject completes the last visit.
PLANNED STUDY DATES: The planned duration of the long-term follow-up is 5 years starting from approximately the end of 2017 and stopping towards the end of 2022.
OBJECTIVES: Primary Objective: To assess the long-term safety of intravitreal GS010 administration up to 5 years post-treatment in subjects who were treated in the RESCUE or REVERSE studies. Secondary Objectives: (1) To assess the long-term efficacy of intravitreal GS010 administration up to 5 years post-treatment in subjects who were treated in the RESCUE or REVERSE studies. (2) To assess the quality of life (QOL) in subjects who were treated with GS010 in the RESCUE or REVERSE studies for up to 5 years post-treatment.
STUDY DESIGN: Background: Subjects with Leber Hereditary Optic Neuropathy (LHON) who participated in the RESCUE and REVERSE clinical trials were administered gene therapy with the investigational medicinal product (IMP), GS010, by a single intravitreal (IVT) injection in a single randomly-selected eye, while the fellow eye received a sham IVT injection. The European Medicines Agency Committee for Medicinal Products for Human Use guideline recommends a monitoring plan for the purpose of observing subjects for potential delayed adverse events (AEs) for up to 5 years post-treatment; hence, the main rationale for initiating this long-term follow-up study. Study Design: This will be a Phase III prospective non-interventional long-term follow-up clinical study of subjects previously treated with GS010 and sham during 2 Phase III studies—RESCUE and REVERSE. The long-term follow-up study will follow subjects over an additional 3 years, for a total of 5 years post-injection follow-up. The long-term follow-up study will include 5 visits at 2, 2.5, 3, 4, and 5 years after IMP injection. Assessments: Safety, efficacy, and QOL variables will be assessed during each of the 5 long-term follow-up visits and descriptive summaries and statistical testing will be used for analysis of the data.
ENDPOINTS: Primary Endpoint 1) Adverse events (AEs) or serious adverse events (SAEs) (ocular or systemic) related to IMP or administration procedure, as judged by the Investigator, reported during the long-term follow-up visits (2, 2.5, 3, 4, and 5 years) from the period of 96 weeks up to 5 years post-treatment and summarized descriptively by type, frequency (number, percentage), severity, causal relationship, and seriousness. Secondary Endpoints 1) Ocular or vision-related adverse events reported during the post-treatment long-term follow-up visits from the period of 96 weeks up to 5 years and summarized descriptively by type, frequency (number, percentage), severity, causal relationship, and seriousness. 2) Change in contrast sensitivity measured with the Pelli-Robson chart in all-, best-, and worst-eyes treated with GS010 IVT injection compared to all-, best-, and worst-eyes treated with sham IVT injection respectively, from the RESCUE or REVERSE study baselines and pooled, to the follow-up study time points (2, 3, 4, and 5 years). 3) Change in best corrected visual acuity (BCVA) reported with Logarithm of the Minimal Angle of Resolution (LogMAR), change of parameters measured with Humphrey™ visual field (HVF) 30-2, and change of parameters measured with spectral-domain optical coherence tomography (SD-OCT) in all-, best- and worst-eyes treated with GS010 IVT injection compared to all-, best-, and worst-eyes treated with sham IVT injection respectively, from the RESCUE or REVERSE study baselines and pooled, to each follow-up study time points (2, 2.5, 3, 4, and 5 years).

- 4) Response status of eyes treated with GS010 IVT injection compared to eyes treated with sham IVT injection, including all-, best- and worst-eyes receiving GS010 or sham respectively, with responder eyes defined by:
 - a. An improvement of at least 15 Early Treatment Diabetic Retinopathy Study (ETDRS) letters (equivalent to a decrease of at least 0.3 LogMAR) compared to baseline, or having a Snellen acuity equivalent better than 20/200. The McNemar test will be used for comparisons from the RESCUE or REVERSE study baselines and pooled, to each of the follow-up study time points (2, 2.5, 3, 4, and 5 years).
 - b. Eyes that lose less than the 15 ETDRS letters (equivalent to an increase of less than 0.3 LogMAR) compared to the RESCUE or REVERSE study baselines and pooled.
- 5) Response status of subjects whose ETDRS scores of the treated eye are at least 15 letters better than the sham eye or whose treated eye has a LogMAR acuity of at least 0.3 LogMAR better than the sham eye at each long-term follow-up visit (2, 2.5, 3, 4, and 5 years) in the RESCUE and REVERSE studies and pooled.
- 6) Time course of the response in eyes treated with GS010 IVT injection compared to eyes treated with sham IVT injection, for the BCVA reported with LogMAR, for parameters measured with HVF 30-2 and for parameters measured with SD-OCT, with comparisons from the RESCUE or REVERSE study baselines and pooled, to each follow-up study time point (2, 2.5, 3, 4, and 5 years) using mixed-effects models with repeated measures (MMRM).
- 7) Time course of the response in eyes treated with GS010 IVT injection compared to eyes treated with sham IVT injection, for contrast sensitivity measured with the Pelli-Robson chart with comparisons from the RESCUE or REVERSE study baselines and pooled, to follow-up study time points (2, 3, 4, and 5 years) using MMRM.
- 8) Visual improvement as measured by LogMAR by analysis of covariance (ANCOVA) to determine the difference in improvement for all-GS010 eyes compared to all-sham eyes, for best-GS010 eyes compared to best-sham eyes and for worst-GS010 eyes compared to worst-sham eyes, with comparisons from the RESCUE or REVERSE study baselines and pooled, to each follow-up study time point (2, 2.5, 3, 4, and 5 years).
- 9) Change of ganglion cell layer thickness/volume and topographical map and other parameters measured by SD-OCT (e.g., retinal nerve fiber layer and quadrantal thickness analyses) for all-GS010 eyes compared to all-sham eyes, for best-GS010 eyes compared to best-sham eyes and for worst-GS010 eyes compared to worst-sham eyes, from the RESCUE or REVERSE study baselines and pooled, to each follow-up study time point (2, 2.5, 3, 4, and 5 years) using MMRM.
- 10) Quality of life as measured with the Visual Functioning Questionnaire 25 (VFQ-25) and 36-Item Short Form Health Survey, version 2 (SF-36-v2) subject-rated instruments and summarized descriptively with within-group comparisons from the RESCUE or REVERSE study baselines and pooled, to each follow-up study time point (2, 2.5, 3, 4, and 5 years).

STUDY POPULATION AND MAIN CRITERIA FOR INCLUSION/EXCLUSION:

The study population will include subjects who were treated with GS010 in either of the 2 Phase III trials—RESCUE and REVERSE. Subjects will have had vision loss and been diagnosed with LHON due to the G11778A point mutation in the mitochondrial *ND4* gene. Subjects will have received a single IVT injection of the gene therapy GS010 in a single randomly-selected eye in the RESCUE or REVERSE studies.

Subjects will provide informed consent and will be enrolled after all inclusion/exclusion criteria are met.

Inclusion Criteria:

1. Subject was treated with GS010 IVT injection in either of the RESCUE or REVERSE Phase III clinical studies.
2. Subject of legal consent age has provided informed consent; subjects that are not of legal consent age have undergone their country-approved clinical trial enrollment consent process.

Exclusion Criteria:

1. Subject is unwilling or unable to comply with the protocol requirements.
2. Subject has any medical or psychological condition that, in the opinion of the Investigator, may compromise his or her safe participation in the study.
3. Subject is taking or intending to take idebenone during the long-term follow-up study period.

NUMBER OF SUBJECTS: The study population is limited to the number of subjects treated in the RESCUE or REVERSE studies.
STUDY TREATMENT: Not applicable. No investigational medicinal product will be administered.
STUDY EVALUATIONS: Safety Variables: The safety variables in this study will be AEs and SAEs. Efficacy Variables: The efficacy variables in this study will be contrast sensitivity using Pelli-Robson; best-corrected visual acuity reported in LogMAR; parameters of HVF and SD-OCT; and general and vision-specific parameters affecting QOL. Quality-of-Life Variables: The general overall QOL variables are physical, social, and emotional functioning, bodily pain, mental health and general health perceptions, and vitality/energy, as judged by the subject. The vision-specific QOL variables are eyesight, eye discomfort, ability to read, seeing close objects, seeing distant objects, nighttime vision, seeing during movement/motion, peripheral vision, color vision, and effect of vision on work activities, as judged by the subject.

TABLE OF CONTENTS

1.	SIGNATURES	2
2.	STUDY SUMMARY	4
3.	LIST OF ABBREVIATIONS AND DEFINITION OF TERMS.....	12
4.	INVESTIGATORS AND STUDY ADMINISTRATIVE STRUCTURE	14
5.	INTRODUCTION	16
5.1	Disease Review	16

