7.5.2 Efficacy Variables

The efficacy variables in this study will be contrast sensitivity; BCVA reported in LogMAR; parameters of HVF and SD-OCT; and general and vision-specific parameters affecting QOL (see Section 7.5.3).

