11.5.2 Secondary Long-term Efficacy Analysis

11.5.2.1 Pelli-Robson Contrast Sensitivity

Mean and standard deviation will be summarized at each follow-up visit, along with change from baseline to each follow-up visit, comparing all-GS010 eyes to all-sham eyes and best-GS010 eyes

to best-sham eyes; and worst-GS010 eyes to worst-sham eyes, using summary statistics for continuous variables.

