6.2 MODIFIED INTENT-TO-TREAT

The Modified Intent-to-Treat (mITT) Population is defined as those subjects who received study medication in RESCUE or REVERSE Phase III studies, consented to be enrolled in this long-term follow-up study, and provide visual acuity data at Visit 2. This population will be used as the primary population for efficacy and QoL analyses. This population is identical to the Safety Population. Missing non-safety endpoints will be imputed with LOCF.

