8.5 EFFICACY ANALYSES

All efficacy analysis will be conducted on the mITT Population, the PP Population, and additionally in subset populations as appropriate. All summaries will be performed on RESCUE separately, REVERSE separately, and on RESCUE and REVERSE combined.

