8.5.2.6 Goldmann Applanation Tonometry

Intraocular pressure (IOP) measurement (mmHg) in each follow-up visit and change from baseline to follow-up visits (Years 2, 2.5, 3, 4, and 5) will be summarized by all-GS010 eyes and all-sham eyes using summary statistics for continuous variables. Ocular and Slit-Lamp Examination

The result (normal/abnormal) before pupil dilation and after dilation for baseline and all follow-up visits (Years 2, 2.5, 3, 4, and 5) will be summarized by all-GS010 eyes and all-sham eyes and anatomical location using counts and percentages.

Quality-of-Life Analyses

Total scores and change of VFQ-25 and SF-36 scores (all individual domains and subdomains) from baseline to each follow-up Visit (Years 2, 3, 4, and 5) for all subjects will be assessed and summarized descriptively. Note that results will be presented in all subjects only, as all subjects are treated with GS010.

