8.6 SAFETY ANALYSES

All safety analysis will be conducted on the Safety Population and summarized by treatment actually received.

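### The SAP files the IOP and slit-lamp visit summaries under secondary efficacy, and its two imputation passages conflict on whether missed examinations are carried forward

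*Protocol*

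**What the plan says.** **Classification.** The protocol's list of safety variables is short: "The safety variables in this study will be AEs and SAEs" (Section 2, repeated in 7.5.1). The efficacy list in Protocol 7.5.2 does not name IOP or slit-lamp findings either: "The efficacy variables in this study will be contrast sensitivity; BCVA reported in LogMAR; parameters of HVF and SD-OCT", followed by quality of life. Both are nevertheless analysed in Protocol 11.5.2.7 and 11.5.2.8, under the parent heading "11.5.2 Secondary Long-term Efficacy Analysis".

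**SAP placement.** SAP 8.5.2.6, within the secondary efficacy variables, covers "Intraocular pressure (IOP) measurement (mmHg) in each follow-up visit and change from baseline to follow-up visits" and, for the slit lamp, "The result (normal/abnormal) before pupil dilation and after dilation for baseline and all follow-up visits". SAP 8.6 covers adverse events, laboratory data, vital signs, physical examination and ECG. It has no IOP or slit-lamp entry, even in 8.6.4, whose title extends to other safety observations.

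**Population.** SAP 8.5: "All efficacy analysis will be conducted on the mITT Population, the PP Population, and additionally in subset populations as appropriate". SAP 8.6: "All safety analysis will be conducted on the Safety Population".

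**Missing data.** SAP 6.2, for mITT: "Missing non-safety endpoints will be imputed with LOCF". SAP 8.5.3 refers to 5.5. There, 5.5.1 states last observation carried forward (LOCF) for a missing LogMAR value, gives contrast sensitivity a rule of its own, and is silent on IOP and slit lamp. SAP 6.3 restricts PP to subjects who completed the follow-up and does not impute.

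**The concern.** The study's primary objective is long-term safety after an intravitreal product. IOP and the slit-lamp examination are objective ocular measurements scheduled at every visit. Protocol 10.3 singles out ocular inflammation as of interest and grades anterior vitreous cells from the slit-lamp examination. SAP 8.7.2 treats IOP elevation and intraocular inflammation as safety topics. Summarising the underlying measurements under efficacy rules is out of step with that.

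The practical risk is a Year 4 or Year 5 row that reports an examination made at an earlier visit, in a table whose denominator does not fall as subjects leave. The PP version avoids imputation but drops everyone who withdrew, and those are the subjects a long-term safety reader would ask about.

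**Working it through.** **1. Which population applies.** Section placement decides this. Both summaries fall under SAP 8.5, so they are run on mITT and PP. Nothing in 8.6 brings them into the Safety Population. SAP 6.2 calls mITT identical to the Safety Population but also requires visual acuity data at Visit 2. Under that condition a subject could leave the IOP and slit-lamp tables for a reason unrelated to safety.

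**2. Which missing-data rule applies.** Two readings are open:

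| Reading | Basis | mITT table at Years 3 to 5 |
|---|---|---|
| A | 6.2: LOCF for whatever is not a safety endpoint | Carried values included, constant denominator |
| B | 8.5.3 and 5.5.1: LOCF for LogMAR only | Observed values only |

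Reading A is supported by the placement under efficacy and by the absence of any exemption. Reading B is supported by 5.5.1 and by the fact that neither measurement is a listed endpoint in SAP 4.1 to 4.3. The text does not settle the choice.

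**3. What reading A would do.** There is no figure in the plan to reproduce: the documents give no number of subjects, dropout rate or abnormal rate. Let d be the share of eyes not examined at a visit, p1 the abnormal rate in examined eyes, p0 the rate the unexamined eyes would have shown, and q the abnormal share among carried values.

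- Rate in all eyes: (1 − d)·p1 + d·p0
- Rate printed under LOCF: (1 − d)·p1 + d·q
- Error: d·(q − p0)

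The sign depends on whether carried values are abnormal less or more often than current ones would have been.

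*All carried values normal (q = 0), dropout uninformative (p0 = p1 = p).* The printed rate is p·(1 − d), a relative understatement of d:

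| Assumed p | d = 10% | d = 20% | d = 30% |
|---|---|---|---|
| 5% | 4.5% | 4.0% | 3.5% |
| 10% | 9.0% | 8.0% | 7.0% |
| 20% | 18.0% | 16.0% | 14.0% |

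*Assumed counts: 60 GS010 eyes, 6 or 12 not examined at Year 5, 6 abnormal among those examined.*

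- Observed: 6/54 = 11.1% or 6/48 = 12.5%.
- LOCF, all carried values normal: 6/60 = 10.0% in both cases.
- LOCF, one third of carried values abnormal: (6 + 2)/60 = 13.3% or (6 + 4)/60 = 16.7%.

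The same table can therefore fall below or above the observed rate.

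*Precision, same assumed counts.* With no abnormal eyes, the one-sided 95% upper bound 1 − 0.05^(1/n) is 4.87% for n = 60, 5.40% for 54 and 6.05% for 48. For mean IOP change (SAP Section 8 plans a 95% interval for changes from baseline), the half-width 1.96/√n in SD units is 0.253, 0.267 and 0.283. Sixty rows that include 12 carried ones would look about 11% more precise than 48 observed ones (0.253/0.283 = 0.89), if the SD is unchanged.

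**4. What would reveal it.** SAP 8.1 gives attendance by visit, and 5.5.1 requires a footnote naming the imputation method. Counts of missing data are planned only for visual acuity and important SD-OCT parameters. SAP 8.6 promises individual listings for laboratory, vital-sign, physical-examination and ECG data, but 8.5.2.6 promises none for IOP or slit lamp.

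**The case against.** The best defence is that carry-forward is not ordered. The efficacy section points to 5.5, where LOCF is written for LogMAR, and IOP and slit-lamp results are not endpoints, so the 6.2 sentence arguably does not reach them. This stands to the extent that a reader may not infer that the SAP directs LOCF for these tables, or that no observed-value table will exist. Under reading B, with mITT equal to the Safety Population as 6.2 asserts, the mITT table would be that table. It does not remove the conflict between 6.2 and 5.5.1.

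A reader might also infer that ocular safety reporting as a whole is affected. It is not. Ocular adverse events are recorded whatever their cause (Protocol 10.1.2), summarised by eye in the Safety Population (SAP 8.6.1), and not subject to LOCF. The treatment summaries for IOP-elevation and inflammation events in SAP 8.7.2 are likewise untouched. Event tables are only a partial substitute, because events are unsolicited and rest on investigator judgement, and they do not show how many eyes were examined.

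A third inference is that the protocol's variable list is the cause and must be amended. Laboratory values, vital signs and ECG are also outside that list, yet SAP 8.6 analyses them as safety data, so the list does not determine placement.

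Finally, withdrawn subjects are to have an early termination visit with the Visit 5 procedures, including tonometry and slit lamp. Except for those lost to follow-up, a carried value would often be an exit examination. That makes it more recent, but it is still not a Year 4 or Year 5 measurement.

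**Conclusion.** The point holds as an unresolved conflict with a safety consequence, confined to two sets of descriptive visit tables. Whether the IOP and slit-lamp tables contain carried values depends on which SAP passage the programmer follows. If 6.2 is followed, the only unimputed alternative is a completers' table.

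A reader might infer that ocular abnormalities will be understated. The documents do not support a direction or a size. The relative understatement equal to the share missing (10% to 30% over the range shown) assumes that every carried value is normal and dropout is uninformative; abnormal carried values reverse it. All counts used above are assumptions. What does not depend on them is that, under 6.2, a value not measured at the visit would be reported there and the denominator would overstate the eyes examined. No hypothesis test and no primary endpoint is involved, so this is a worthwhile correction rather than a threat to the study's main conclusion.

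**What to change.** Change the SAP only:

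- Move the IOP and slit-lamp summaries from 8.5.2.6 to 8.6.4.
- Analyse them in the Safety Population by eye, with observed values only and the number of eyes examined at each visit as denominator.
- In 6.2, limit the LOCF sentence to named efficacy endpoints, consistent with 5.5.1.

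This also frees both tables from the Visit 2 acuity condition and from the completer restriction. The cost is SAP wording and re-pointing two table shells; no new data are needed. The one downside is that n falls at later visits, which is what the reader needs to see. No protocol amendment is required.

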3. LIST OF ABBREVIATIONS AND DEFINITION OF TERMS

Abbreviation	Word or Phrase
AAV	adeno-associated virus(es)
AAV2/2	adenovirus-associated viral vector serotype 2
AE	adverse event
ANCOVA	analysis of covariance
ATC	Anatomical Therapeutic Chemical
BCVA	best-corrected visual acuity
CBER	Center for Biologics Evaluation and Research (FDA)
CF	count fingers
CFR	Code of Federal Regulations
CHMP	Committee for Medicinal Products for Human (EU)
CRF	case report form
CRA	clinical research associate
CRO	contract research organization
CTCAE	Common Terminology Criteria for Adverse Events
eCRF	electronic case report form
EMA	European Medicines Agency
EOS	end of study
ETDRS	Early Treatment Diabetic Retinopathy Study
ETV	early termination visit
EU	European Union
FDA	Food and Drug Administration (United States)
GCL	ganglion cell layer
GCP	Good Clinical Practice
HVF	Humphrey™ visual field (test)
ICF	informed consent form
ICH	International Council for Harmonisation
IEC	independent ethics committee
IMP	investigational medicinal product
IOP	intraocular pressure
IRB	institutional review board
ITT	intent-to-treat (population)
IVT	intravitreal
LHON	Leber Hereditary Optic Neuropathy
LogCS	logarithm of contrast sensitivity
LogMAR	Logarithm of the Minimal Angle of Resolution

Abbreviation	Word or Phrase
MedDRA	Medical Dictionary for Regulatory Activities
MMRM	mixed-effects models with repeated measures
mtDNA	mitochondrial DNA
NIH	National Institutes of Health
OCT	optical coherence tomography
QOL	quality of life
rAAV2	recombinant adeno-associated virus 2
RNFL	retinal nerve fiber layer
SAE	serious adverse event
SAP	statistical analysis plan
SD-OCT	spectral domain optical coherence tomography
SF-36-v2	36-Item Short Form Health Survey, version 2
SLE	slit-lamp examination
SOP	standard operating procedure
SUN	Standardization of Uveitis Nomenclature
US/USA	United States/United States of America
VFQ-25	Visual Function Questionnaire 25
WHO	World Health Organization

5. INTRODUCTION

5.1 Disease Review

Leber Hereditary Optic Neuropathy (LHON) is a rare, maternally inherited mitochondrial genetic disease, typically presenting as a non-syndromic optic neuropathy. Retinal ganglion cells (RGC), whose axons form the optic nerve, are the major cellular target affected by the resultant mitochondrial dysfunction. LHON was the first inherited human disease associated with point mutations in the mitochondrial DNA (mtDNA)¹ and it is considered the most common inherited genetic mitochondrial disorder.² LHON is a rare disease, and in Northern Europe, an estimated prevalence ranging from 1 in 30,000 to 1 in 50,000 has been reported.³⁻⁵

Three primary point mutations in the mtDNA are causative of LHON in approximately 90% of those affected. These point mutations, G3460A, G11778A and T14484C, occur respectively in the *ND1*, *ND4*, and *ND6* genes of the mtDNA, and all encode protein subunits of Complex I (CI) of the mitochondrial respiratory chain. The resultant dysfunction of CI and the respiratory chain lead to abnormal mitochondrial metabolic function, decreased adenosine triphosphate (ATP) production, and increased reactive oxygen species. This leads to cell death of the RGC and the resulting atrophy of the optic nerve.³

LHON manifests as acute to sub-acute, sequential, bilateral, painless vision loss. It is a bilateral disease, and the clinical manifestation is essentially predictive of bilateral involvement. Greater than 97% of patients are reported to have bilateral involvement at 12 months and occurrences of unilateral involvement in retrospective reports of cohorts with LHON are very rare.^{6,7} A G11778A *ND4* cohort was studied in which 53% reported bilateral involvement in ≤ 2 months, and 80% reported bilateral involvement in ≤ 6 months.⁸

The clinical hallmark of LHON is central vision loss.⁹ This is accompanied by dysfunction of color and contrast vision and central and cecentral visual field defects and a final visual acuity of 20/200 or worse in 98% of eyes.^{6,10} A prospective natural history study⁸ reported LHON subjects with the G11778A *ND4* mutation. The primary outcome was the finding of no significant difference in the Early Treatment Diabetic Retinopathy Study (ETDRS) visual acuity at 12, 24, or 36 months of follow-up compared to baseline at study entry. This finding was for the entire cohort as well as for the subgroups of patients who entered the study within 12 months of disease onset or after 12 months of disease onset. Improvement by ≥ 15 ETDRS letters occurred in 14.7% of total study eyes in 18% of study patients over the study period. Eighty-six percent of patients had eyes with stable acuities during study follow-up. Subjects entering the study after 36 months from disease onset showed no change or improvement of visual acuity over follow-up. The authors concluded that for the G11778A *ND4* mutation spontaneous natural recovery is partial and occurs on a very limited basis in a small percentage of subjects, and thus, gene therapy interventions can be measured for efficacy with a reasonable sample size.

5.2 Long-term Follow-up of the Benefits and Risks of Study Treatment Investigational Medicinal Product

This long-term follow-up study will be non-interventional hence, no investigational medicinal product (IMP) will be administered. GS010 was administered to subjects via standard intravitreal (IVT) injection in RESCUE or REVERSE. Please see the Phase III study protocols

or the Investigator's Brochure for a discussion of the IMP.

Generation of GS010 Safety Profile

For the profile of GS010 including the expected adverse events, please refer to the current version of the Investigator's Brochure. Investigators are also referred to Van Der Reis¹¹ and Jager¹² for review of IVT injection-associated adverse effects.

